7.4.4 Safety Laboratory Assessments

Blood samples and optional urine samples will be collected for routine safety laboratory tests (hematology, serum biochemistry, and urinalysis) at Visit 1 (Screening), Visit 3 (Week 4), Visit 5/End of Double-blind Treatment, Visit 6 (Week 16), Visit 8 (Week 24) or at early termination from the study. Clinical laboratory specimens will be analyzed by a central licensed and accredited laboratory facility according to the laboratory's standard operating procedures (For China, clinical laboratory specimens will be analyzed by local lab). The following tests will be performed:

Hematology: hemoglobin, hematocrit, red blood cell (RBC) count, white blood cell (WBC) count with differential, and platelet count, mean corpuscular hemoglobin (MCH), mean corpuscular hemoglobin concentration (MCHC), mean corpuscular volume (MCV)

Serum chemistry: glucose (non-fasting, but for China, glucose will be tested under fasting state), blood urea nitrogen (BUN), creatinine, aspartate aminotransferase (AST), alanine aminotransferase (ALT), alkaline phosphatase, sodium, potassium, chloride, calcium, phosphorus, bicarbonate, uric acid, lactic dehydrogenase (LDH), total protein, albumin, bilirubin (total and direct), total cholesterol, triglycerides

Urinalysis: color/appearance, pH, specific gravity, glucose, ketones, protein, and microscopic appearance.

The investigator may collect additional blood or urine samples to repeat any laboratory test that was abnormal post-dosing, was within normal limits at Baseline, and is considered clinically significant. Abnormal laboratory results at the last scheduled visit may require additional collection of samples on an "as needed" basis until: a) the values return to the baseline value, b) the values are within normal limits, c) the values are clinically stable, or d) the investigator determines that further follow-up is unnecessary. The investigator will record the date and time of

all additional samples collected. If the investigator establishes a clear explanation for the laboratory abnormality, he or she will record this explanation in the CRFs.

7.4.5 Pregnancy Testing

Female subjects of child-bearing potential will undergo a UPT at the screening visit before any study-specific procedures are performed. If the UPT is positive, the subject will not be permitted to enroll in the study. In the unlikely event that a urine pregnancy test cannot be obtained, a serum pregnancy test can be run from the serum sample collected.

Pregnancy tests will be performed at all clinic study visits on female subjects of child-bearing potential. The pregnancy tests must have a sensitivity of at least 25 mIU/mL. If there is a suspicion of pregnancy at any time during the study, a urine sample will be obtained and tested. Should a subject become pregnant during the study, treatment must be discontinued. Subjects should continue with non-treatment and/or follow-up visits. For China, different pregnancy test procedure would be followed.

All pregnancies should be immediately reported to the sponsor/Contract Research Organization (CRO)/Medical Monitor and followed through to resolution (i.e., delivery, miscarriage, or abortion). The report should be submitted within the same timelines as an SAE (within 24 hours of knowledge), although a pregnancy per se is not considered an SAE. Information on the status of the fetus and the mother may be requested (see Section 7.4.2) to include outcome of delivery.

If the pregnancy is associated with an SAE (e.g., if the mother is hospitalized for dehydration), in addition to the pregnancy report form, a separate SAE report form must be filed. Miscarriage, stillbirth and any malformation/disease must be reported as a SAE. Any pregnancy leads to the immediate cessation of the study treatment.

7.4.6 Vital Signs

Measurements of vital signs, including blood pressure, pulse rate, and respiratory rate, will be taken at every clinic visit with the subject seated.

7.4.7 Physical Examination

At the screening visit, Visit 8, and Early Termination visits, the investigator or designee will complete an abbreviated general physical examination including measurements of weight (in pounds) and height (inches).

7.4.8 Pharmacokinetics

A single blood sample will be collected at Visit 3 (Week 4/Day 28) during the double-blind treatment period for plasma sirolimus determination.

The actual collection time of the blood sample must be recorded in the source data, collection tube and in the eCRF. Exact prior dosing must be recorded in the source data and in the eCRF.

The central laboratory will provide all materials and supplies to be used for the collection and shipment of biological samples.

Plasma samples for study medication measurements will be stored at the investigational site and shipped as specified in the study lab manual. Plasma samples will be packaged and shipped directly to the bioanalytical laboratory. Specific details on sample collection, processing, aliquoting, storage, and shipping instructions are provided in the laboratory manual.

Plasma sample PK analysis will be performed using validated procedures and methods.

7.5 Appropriateness of Measurements

The safety evaluations are the standardized and most widely accepted methods for evaluating safety in clinical trials. Methodology for evaluating efficacy in the treatment of TSC-related facial angiofibromas are not well established; the methodology in this study was developed according to reports in the literature.⁸⁻¹⁸

8.0 STATISTICAL METHODS AND DETERMINATION OF SAMPLE SIZE STATISTICAL AND ANALYTICAL PLANS

8.1 General Considerations for Data Analysis

The methodology presented below represents a brief overview of the statistical methods that will be fully detailed in the statistical analysis plan (SAP). The SAP will be finalized before the database is locked and unblinded. Any changes to the methods described in the final SAP will be described and justified in the clinical study report. It is planned that the data from all centers that participate in this protocol will be combined so that an adequate number of subjects will be available for analysis. All statistical analyses will be performed using SAS statistical software (Version 9.2 above).

Statistical significance will be tested at the 2-sided 5% level. No adjustments for multiplicity are planned.

All efficacy and safety analyses will be performed on observed data with no imputation unless otherwise specified. For the analyses of treatment response, subjects having a missing responder status will be analyzed as non-responders.

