4.0 STUDY DESIGN

4.1 Overall Study Design

This is a Phase 2, randomized, double-blind, placebo-controlled, multicenter study designed to assess the safety and efficacy of topically-applied sirolimus for the treatment of cutaneous angiofibromas in pediatric and adolescent subjects with tuberous sclerosis complex (TSC) with an option to enter an open-label treatment phase. Study subjects will be enrolled at investigational sites in the United States (US) and China, though other countries may be included. Approximately 45 subjects who meet the study entry criteria will be randomly assigned in a 1:1:1 ratio to receive 1 of 3 treatments: sirolimus 0.2% ointment, sirolimus 0.4% ointment, or placebo ointment. The randomization is stratified by site. Subjects will apply the study medication topically to the cutaneous angiofibromas on the face once daily at night for 12 weeks. Subjects who complete the double-blind phase of the study, with an overall compliance rate >80% as determined by the dosing diary, will be offered entry into the open-label period for an additional 12 weeks.

[figure not shown]
The maximum study duration for each subject will be approximately 30 weeks and includes a screening period of up to 4 weeks, a blinded treatment period of 12 weeks, optional open-label period of 12 weeks, and a follow-up period of 2 weeks. After the parent/guardian has provided written informed consent and the subject has assented (for subjects younger than 18 years) or after the subject has provided informed consent (for subjects 18 years of age), the subject will undergo screening procedures.

At the end of the screening period, eligible subjects will be randomly assigned to one of the study treatment groups on Day 1 (Baseline) of the treatment period. The randomization is stratified by site.

[figure not shown]

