6.4 Assignment to Treatment

6.4.1 Randomization

At the Screening Visit and throughout the trial, subjects will be identified by a subject number that will consist of the three-digit site number and a three-digit sequential number, beginning with 001. Site numbers will be 100-1500.

A subject who fulfills the trial eligibility requirements will be randomly assigned to treatment at the Baseline visit. Treatment assignment to randomization numbers will be stratified at the site level. Both the kit and treatment tubes within a kit will have a label containing the randomization number for the double-blind treatment period. When a subject is to be randomized, site personnel will sequentially choose the kit with the lowest randomization number from their stock of double-blind kits, unless otherwise instructed by the study team.

Randomization data will be kept strictly confidential, accessible only to authorized persons as defined below, until the time of unblinding.

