8.5.1 Primary Efficacy Endpoint(s)

The primary efficacy endpoint will be the proportion of subjects with a clinical response of treatment success on Week 12. Treatment success is defined as:

At least a 2-grade improvement on the Week 12 Investigator Global Assessment (IGA) of the facial skin lesions assessed by investigator. The primary efficacy endpoint will be analyzed using Fisher's exact test, making all pairwise treatment comparisons.

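### Randomisation is stratified by site, but the primary and binary secondary endpoints are compared with a pooled Fisher test: a cost in efficiency, not in validity

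*Combined protocol and SAP*

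**What the plan says.** Section 6.4.1: "Treatment assignment to randomization numbers will be stratified at the site level". The synopsis and section 4.1 also state that randomisation is stratified by site. On size, section 4.1 says: "Approximately 45 subjects who meet the study entry criteria will be randomly assigned in a 1:1:1 ratio to receive 1 of 3 treatments". The synopsis allows up to 15 sites in the United States and China, with other countries possible later.

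Section 8.5.1: "The primary efficacy endpoint will be analyzed using Fisher's exact test, making all pairwise treatment comparisons". Section 8.5.2 applies the same test to the binary secondary endpoints. Neither section names site or country as a stratum, in a main or a sensitivity analysis. Section 8.1 adds that "data from all centers that participate in this protocol will be combined", that "Statistical significance will be tested at the 2-sided 5% level" and that "No adjustments for multiplicity are planned".

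Section 8.2 calls the study exploratory, says the sample size has no statistical basis, and says no data exist on which to base a treatment difference. No power, response rate, block size or country split is given.

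**The concern.** When allocation is balanced within a factor that predicts outcome, an analysis that ignores the factor treats between-stratum variation as noise. The test is then more conservative than it need be. Here that comes on top of Fisher's conservatism at about 15 per arm, in a trial with little information to spare.

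Site is too fine to use directly, but sites nest in country. The IGA is a subjective grade of redness and lesion extent (section 7.3.1), and section 7.5 says efficacy methods in this disease are not well established. Response or grading might therefore differ by country. At stake is some power on the primary and binary secondary comparisons, and a treatment estimate that respects the design. Combining centres is not the fault, because a stratified test combines them too. The gap is the missing stratum in sections 8.5.1 and 8.5.2.

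**Working it through.** **Inputs from the documents.** About 45 subjects at 1:1:1, so 45/3 = 15 per arm and 15 v 15 in each comparison; two-sided 5%; no multiplicity adjustment; up to 15 sites; two named countries; missing status counted as non-response, so denominators stay whole. The plan states no power figure to reproduce.

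**Assumptions.** All response rates are assumed. The country split per arm is assumed to be 8/7, with other splits as a check.

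**Why not stratify by site.** 45/15 = 3 subjects per site, and a pairwise comparison keeps two of three arms: 30/15 = 2 per site.

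**Mechanism.** Suppose response goes from 10% to 50% in one country and from 50% to 90% in the other, split 8/7.

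- Pooled placebo rate: (8×0.10 + 7×0.50)/15 = 0.287. Pooled active rate: (8×0.50 + 7×0.90)/15 = 0.687.
- Variance implied by pooling: 0.287×0.713 + 0.687×0.313 = 0.42.
- Variance within countries: (8×0.09 + 7×0.25)/15 + (8×0.25 + 7×0.09)/15 = 0.165 + 0.175 = 0.34.
- √(0.42/0.34) = 1.11, so pooling overstates the standard error of the difference by about 11%.

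**Tests.** In stratum h, given t_h responders among n_h active and m_h placebo subjects, the number of active responders is hypergeometric (n_h + m_h, t_h, n_h). Convolving over strata gives the null distribution of the total S. The two-sided exact p is the sum of P(s) over all s with P(s) ≤ P(s_obs). Mid-P counts only half the probability of outcomes tied with the observed one. Fisher's test is the one-stratum case.

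**Power by full enumeration, 15 v 15, split 8/7 (%).**

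| Assumed response, placebo to active, by country | Fisher | Pooled mid-P | Stratified exact | Stratified mid-P |
|---|---|---|---|---|
| 10 to 55 in both | 64 | 77 | 66 | 77 |
| 10 to 50; 20 to 60 | 48 | 62 | 50 | 63 |
| 5 to 40; 30 to 80 | 50 | 66 | 60 | 72 |
| 10 to 50; 50 to 90 | 42 | 59 | 55 | 67 |

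**Stratified exact minus Fisher (like for like).** The gain is about 1 to 2 points in the first two rows, about 9 in the third (before rounding) and 13 in the fourth. With countries 20 points apart (10 to 50; 30 to 70) it is about 3 points at 8/7 and about 5 at 10/5. With 5 to 40 and 25 to 70, where the gap is 20 points on placebo and 30 on active, it is 4.6 to 6.5 points across splits 8/7, 10/5 and 12/3. At 10/5 the fourth row goes from 42.4 to 55.7. The difference was never negative.

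**Pooled mid-P minus Fisher (no strata at all).** In the table the gain is 77−64 = 13, 62−48 = 14, 66−50 = 16 and 59−42 = 17 points. Over all runs it is about 12 to 18.

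**Stratified minus pooled mid-P (effect of the strata).** The gain is 0, 1, 6 and 8 points. Over all runs it is about 0 to 2 when countries are alike or up to 20 points apart, and about 6 to 8 at 25 to 40.

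**Type I error per comparison.** Over a grid of null rates that included unequal country rates, the maximum was 1.8% for Fisher, 2.3% for stratified exact and 4.4% for stratified mid-P. Further runs of stratified mid-P reached 5.1%.

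**The case against.** The case for leaving the plan alone has weight.

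- The study is exploratory with no power target, and pooled Fisher controls its error. This stands, and it limits the point to efficiency.
- Country is not the randomisation stratum, and further countries may be added. This also stands. Country is a workable coarsening of site, chosen because site is too sparse.
- The documents do not show that countries respond differently. The differences they state for China are local laboratories (section 7.4.4) and photograph handling (Appendix 2). Neither bears on the investigator's IGA, which uses one common scale. The 25 to 40 point gaps are therefore assumptions.
- Section 8.1 calls its methods an overview, with detail left to a SAP that is finalised before unblinding. A stratified analysis could still be added there, but the text names none.

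Two stronger readings are tempting. A reader who sets Fisher beside stratified mid-P in the table sees gaps of 77−64 = 13, 63−48 = 15, 72−50 = 22 and 67−42 = 25 points, and might blame them all on the missing stratum. The documents do not support that: they give no rates, and pooled mid-P alone recovers 13 to 17 of those points. A reader might also infer that ignoring the stratum invalidates the test or inflates false positives. It does neither.

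**Conclusion.** The mismatch between design and analysis is real, and its cost is efficiency. An exact country-stratified test gains about 1 to 5 points of power over pooled Fisher if countries differ by 0 to 20 points, and about 9 to 13 points if they differ by 25 to 40, with no loss in the scenarios run. These figures rest on 15 per arm, two countries with a similar split in each arm, and assumed response rates; the plan supplies neither rates nor split. Fisher's conservatism is a separate and mostly larger effect, and should not be counted as a loss from omitting strata.

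**What to change.** In sections 8.5.1 and 8.5.2, and in the matching synopsis text:

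1. Analyse the primary and binary secondary endpoints with an exact Cochran-Mantel-Haenszel test stratified by country, sites pooled within country, for each pairwise comparison.
2. Report a country-stratified risk difference with 95% CI, naming the method.
3. Keep the pooled Fisher test as a prespecified sensitivity analysis.
4. State before unblinding how any added country enters the strata.

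If the mid-P form is preferred, declare it as a separate choice and state its downside. Each comparison uses more of its 5%, and 5% is not strictly guaranteed. With no treatment effect, the family-wise error over the three unadjusted comparisons stayed below 5% with Fisher in simulation, but reached about 11% with stratified mid-P. The fully exact form keeps the strict 5% per comparison.

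The cost is protocol and SAP wording only. No new data, visits or subjects are needed, provided the change is made before the Week 12 lock and unblinding described in section 8.4.

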8.2 Sample Size and Power Considerations

This study is exploratory in nature and the sample size is not based on a statistical rationale. For sample size calculation, reliable assumptions on the difference between treatments for the primary efficacy parameter must be present. However, currently no such data in subjects with TSC are available for sirolimus. Therefore, practical considerations were used for sample size calculation. The planned number of 45 subjects is considered to be sufficient to provide a reliable answer on the efficacy of sirolimus in concentrations of 0.2% and 0.4% in subjects with TSC compared to placebo (in a 1:1:1 ratio) and to achieve insight into the safety of sirolimus.

8.3 Analysis Populations

The primary statistical analyses will be performed on the Intent-to-Treat (ITT) population (efficacy), Per-Protocol population (efficacy) and Safety population (safety). The analysis populations are defined as:

- Intent-to-Treatment (ITT) population will include all randomized subjects. This will be the population for efficacy analysis.
- The Per-Protocol (PP) population will include all ITT subjects with no major protocol deviation and with >80% study drug compliance rate, where the drug compliance will only apply to active treatment groups. Efficacy analyses will be repeated on this population as a sensitivity analysis.
- Safety population will include all subjects who were randomized and dispensed the study medication at Randomization / Day 1, excluding subjects who return all of the study medication unused. This will be the population for safety analysis.

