6.9 Treatment Compliance

Records of study product used and dosages administered will be kept during the study. Product accountability will be checked by the study monitor during site visits and at the completion of the trial.

The tubes of study medication will be weighed prior to dispensation to the subject. Subjects will be asked to return all unopened, partially used and empty ointment tubes to the study site at each clinic visit. The tubes will be weighed and the weight difference will be analyzed as a measure of product usage. Subjects or their parent/guardian will be asked to complete a simple dosing diary on a daily basis recording the times at which they administered the treatments. A missed dose should also be recorded upon realization that the dose was missed.

Compliance at each visit will be determined as follows:

(# of Dose Days / Total # of Days between visits) * 100

Subjects who are estimated to have missed on average >1.5 doses per week, as recorded in the dosing diary, will be considered non-compliant. All attempts should be made to improve the subject's compliance, including counseling. Subjects may be withdrawn/early terminated from the study due to non-compliance.

An overall compliance rate will be calculated for the double-blind treatment period, at the conclusion of Visit 5, to determine the subject's eligibility for the open-label treatment period. Subjects with an overall compliance rate that is > 80%, as determined by the dosing diary, will be allowed to continue on to the open-label phase of the trial.

Investigators may temporarily suspend dosing at their discretion, however the time subject is off study drug should be minimized. If study drug use is suspended more than 7 days (consecutive or in aggregate in either the double-blind or open-label phase of the trial), the investigator should contact the Medical Monitor to review medical reasons and steps to be taken to assure patient's adherence to study requirements. The exact dates of investigator approved stopping and re-starting study drug will be recorded in the CRF. Investigator initiated suspension of study drug will not count toward overall compliance.

Subjects will be asked to return all unused product at the end of the study.

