8.4 Interim Analysis

One interim analysis will be performed.

The interim analysis will be conducted by the study team when all subjects have completed the double-blind phase (Visit 5 - Week 12). The database will be locked and unblinded to assess for efficacy and safety. The results will be reported in the clinical study report (CSR).

In the event of early stopping due to interim analysis results, subjects will be brought to the investigational sites for a final visit. The final analysis will include all data collected up to and including the final visit.

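### The per-protocol set applies the >80% compliance condition to the sirolimus arms only, so its active-versus-placebo comparisons are biased if compliance is prognostic for response

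*Combined protocol and SAP*

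**What the plan says.** Section 8.3 defines PP as ITT subjects with no major protocol deviation and "with >80% study drug compliance rate, where the drug compliance will only apply to active treatment groups". It gives no reason for exempting placebo. On the role of PP it says: "Efficacy analyses will be repeated on this population as a sensitivity analysis". The ITT bullet makes ITT the efficacy population, but the lead sentence of the same section reads: "The primary statistical analyses will be performed on the Intent-to-Treat (ITT) population (efficacy), Per-Protocol population (efficacy) and Safety population (safety".

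Section 6.9 measures compliance in every arm: "Subjects or their parent/guardian will be asked to complete a simple dosing diary on a daily basis". Compliance is the number of dosing days divided by the days between visits. The same >80% diary threshold decides open-label entry for all double-blind subjects, placebo included. Section 6.9 also says: "Subjects may be withdrawn/early terminated from the study due to non-compliance".

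Section 8.1 says that "subjects having a missing responder status will be analyzed as non-responders". Section 8.4 places an analysis by the study team after all subjects have completed Week 12: "The database will be locked and unblinded to assess for efficacy and safety".

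**The concern.** The compliance condition is a post-randomisation exclusion made in two of three arms. Each active-versus-placebo PP comparison therefore sets compliers on sirolimus against compliers and non-compliers together on placebo. If subjects who keep to the regimen would do better, or be assessed more completely, whatever they were given, the two groups differ before any drug effect.

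The plan contains one route by which this could happen. A poorly compliant subject may be withdrawn (6.9), and missing responder status then counts as failure (8.1). On sirolimus, the compliance condition can remove that subject from PP. On placebo, the same subject can remain as a non-responder.

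PP is the only sensitivity population named for efficacy. If PP agrees with ITT, or shows a larger effect, part of that could come from the filter, and a reader could not tell how much. In addition, membership depends on the arm, so the compliance part of PP cannot be settled while the data are blinded.

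**Working it through.** **Inputs from the document**
- 45 subjects at 1:1:1 (4.1, 8.2), so 45/3 = 15 per arm.
- Fisher's exact test, pairwise (8.5.1), two-sided 5%, no multiplicity adjustment (8.1).
- The compliance condition applies to the active arms only (8.3).

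Section 8.2 says the sample size has no statistical basis, and the document gives no expected response or compliance rate. There is no planned figure to reproduce.

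**Assumptions**
- No drug effect, and equal compliance in all arms.
- No other PP exclusions.
- Share of non-compliers q = 10%, 20% or 30%.
- Complier response rc = 10%, 20%, 30%, 40% or 50%.
- Non-complier response rn = 0, rc/2 or rc.

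This gives 3 × 5 × 3 = 45 combinations.

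**False difference**
- Active PP rate = rc.
- Placebo PP rate = (1 − q) × rc + q × rn.
- Difference = q × (rc − rn).

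With q = 0.2 and rn = 0:

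| rc | Active PP | Placebo PP | Difference | Subjects in 15 |
|---|---|---|---|---|
| 10% | 10% | 8% | 2 points | 0.3 |
| 20% | 20% | 16% | 4 points | 0.6 |
| 40% | 40% | 32% | 8 points | 1.2 |

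The largest value on the grid is 0.3 × (0.5 − 0) = 15 points, and the smallest is 0, at rn = rc. Outside the grid the sign can turn: q = 0.2, rc = 20%, rn = 40% gives 0.2 × (0.2 − 0.4) = −4 points, against sirolimus.

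In whole subjects, suppose each arm of 15 has 12 compliers with 6 responses and 3 non-compliers with none. ITT compares 6/15 with 6/15. PP as written compares 6/12 (50%) with 6/15 (40%).

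**False wins for sirolimus**

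These come from exact enumeration of the two-sided Fisher test. The number of compliers in a filtered arm is binomial (15, 1 − q), and placebo stays at 15 under the rule as written. All rows have q = 0.2. The middle column keeps the rule as written but sets rn = rc, so it shows what the unequal group sizes do with no bias present.

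| rc | As written, rn = 0 | As written, rn = rc (no bias) | Filter in all arms |
|---|---|---|---|
| 10% | 0.86% | 0.63% | 0.32% |
| 20% | 2.34% | 1.29% | 1.01% |
| 40% | 3.85% | 1.42% | 1.50% |

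At rc = 10%, bias accounts for 0.86 − 0.63 = 0.23 of the 0.86 − 0.32 = 0.54 point rise. The rest is the larger placebo group. At 20% it accounts for 1.05 of 1.33 points, and at 40% for the whole rise. The error is also lopsided: at rc = 40% and rn = 0, false wins for placebo are 0.44%.

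Over the 45 combinations, the total two-sided false-positive rate under the rule as written is 0.8% to 8.1%. It exceeds 5% in two of them, both with q = 30% and rn = 0: 6.45% at rc = 40% and 8.12% at rc = 50%.

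**The case against.** The strongest reply is that little depends on PP. ITT is the efficacy population, PP is a repeat, and section 8.2 calls the study exploratory. The total error rate stays below 5% in 43 of the 45 combinations, and if the placebo response is low the false difference is only a few points. This stands and limits the severity. It does not restore PP as a check on ITT: the chance of a false win for sirolimus exceeds 2.5% in 11 of the 45.

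A second reply is that placebo compliance has no pharmacological meaning. If non-compliers respond less only because they applied less drug, compliant sirolimus subjects against all placebo is not a biased estimate of the effect in compliers. This is correct, and it is why the concern is confined to a prognostic link. An arm-specific filter cannot separate the two mechanisms, and the withdrawal route does not depend on drug exposure.

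Third, the direction is not established. Major protocol deviation is not defined in section 8.3, so early withdrawals might leave PP in every arm. Section 6.9 gives no compliance denominator for subjects who stop early, so some might pass >80% over their time on treatment. This also stands: the bias may favour sirolimus, and no more than that can be said.

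Finally, section 8.1 calls section 8 an overview, with detail to follow in a SAP finalised before unblinding. The denominator and the timing of PP membership could be settled there. The active-only clause is an explicit rule, not a missing detail, so this does not excuse it.

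**Conclusion.** The concern holds. As written, PP selects the active and placebo groups by different rules, although the data for a common rule are collected in every arm. Under the stated assumptions the false difference is 0 to 15 points. With 20% non-compliers who never respond, it is 2 to 8 points at complier response of 10% to 40%. Every rate is assumed, and the size and sign depend on how compliance relates to response apart from drug exposure. The damage is confined to the PP active-versus-placebo comparisons, so this should be fixed but does not threaten the primary ITT result. A common filter removes the bias made by the rule itself. It does not give full protection if treatment affects compliance, because compliance is measured after randomisation.

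**What to change.** In section 8.3, delete the clause restricting the compliance condition to the active groups, and apply the same >80% diary criterion to all three arms. Settle PP membership for every subject before the Week 12 unblinding in section 8.4, which a common rule makes possible under blind.

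Two smaller items can be handled in the same edit or in the SAP:
- State the compliance denominator for subjects who stop before Visit 5.
- Reword the lead sentence of 8.3 to agree with its bullets, with ITT primary for efficacy and PP a sensitivity analysis.

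The cost is one clause and one sentence, carried into the SAP, with no new data collection. The placebo PP group may lose a few subjects, about 0.2 × 15 = 3 at 20% non-compliance.
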